# 1.12 Managing donor milk and formula availability in the well baby unit

#### 1.12.1 Human Donor Milk Handling:

The preparation of human donor milk occurs daily at the milk bank in room 4. After thawing, the milk is aliquoted into 12 syringes, each containing 10 ml, as part of the daily routine. Subsequently, study staff transports these aliquoted syringes to the well-baby unit on a daily basis. The storage of these aliquots is carried out within a dedicated fridge, specifically allocated for the CanDo trial, located in the medication room within the well-baby unit. This setup is designed to ensure convenient and immediate access for nurses when administering donor milk as a supplementation to infants.

In addition, it is the responsibility of the study staff to ensure that the donor milk log sheet is completed at each shift by the nurse caring for the infant.

#### 1.12.2 Formula Supplementation:

When an infant is randomized to receive formula, the nursing team will utilize the formula resources present within the well baby unit. They will follow established unit procedures to obtain the necessary formula, which includes accessing formula resources in accordance with the standard storage process as required. This aligns with the hospital's typical policy for formula provision and handling.

#### 1.12.3 Inventory and Record Keeping:

An inventory and comprehensive record will be maintained to ensure thorough oversight of both human donor milk and formula dispensed to infants. This meticulous record-keeping will be managed through the maintenance of a readily accessible log sheet. This practice safeguards the accuracy of documentation related to the supplements given to infants.

In summary, this comprehensive approach ensures the availability of both human donor milk and formula for supplementation within the well baby unit. The detailed procedures outlined herein, in conjunction with the diligent inventory and record-keeping practices, establish a systematic plan to fulfill the supplementation needs of the study.

# 1.13 Data Storage and Security:

Regarding data security, our study is committed to ensuring the protection of computerized data. We have implemented the following measures to secure all data, including hospital and study visit information: All data, including hospital and study visit information, will be securely stored on the Mount Sinai server. Access to this data will be limited to authorized study team members to ensure confidentiality and data protection. Data security measures, including password protection and access restrictions, will prevent unauthorized access or manipulation of the data.

#### 1.13.1 Survey Data Using REDCap:

Data collected during the study will be securely managed using the REDCap platform hosted on the University of Toronto's server. This setup ensures robust security during data collection. After completing data collection, all information will be securely transferred to the Mount Sinai Hospital server for storage, maintaining the highest level of data security and confidentiality.

#### 1.13.2 Data Sharing and Collaboration Agreement:

A Data Sharing and Collaboration Agreement has been established between the University of Toronto and Mount Sinai Hospital. This agreement formalizes data sharing procedures, specifying terms and conditions. It ensures compliance with data protection regulations and ethical considerations, providing a framework for secure and responsible data sharing between the two institutions. These measures collectively safeguard the computerized data collected during our study, ensuring its integrity and confidentiality. We prioritize the security of participant information and data throughout the research process.

#### 1.14 Health service research issues to be addressed

The use of human donor milk nearly ceased at the time of the HIV epidemic. During the current era of neonatal care and the appreciation of human milk and its health protective effects, donor milk use is growing exponentially. Although there are no statistics from Canadian well-baby units, two surveys from the United States document rapid increases in donor milk programs in well-baby units despite a lack of evidence. It is important to emphasize the timeliness of conducting an RCT to investigate the use of donor milk for this specific group of infants. Simultaneously, studying the associated health economics and health services is equally important. The majority of infants in Canada are admitted to a well-baby unit and many require supplementation while in hospital which is known to be one of the strongest predictors of non-exclusive human milk feeding in the long-term with its consequent negative health impacts. A change in policy of method of supplementation during initial hospitalization must thus be well researched prior to implementation as it may be an important public health initiative, or it may be costly without benefit.

# 1.15 Expected project deliverables

The proposed trial will provide enough data to either support or refute the need for improved access to donor milk in well-baby units. At present, 5 of 52 well-baby units in Ontario offer donor milk supplementation. It is anticipated that positive results from this trial may be utilized to advocate for greater equity in accessing donor milk in all well-baby units. On the other hand, null or negative trial results may call into question the use of donor milk for this population of infants and may suggest redirection of funds to other programs within a well-baby unit. The carefully selected secondary and exploratory outcome variables will provide evidence for the importance of nutrition on early parent-child interactions and subsequent infant health, growth and development. As this early period in child development is believed to have a significant impact on life-long health and well-being, the importance of research in supporting families during this time period cannot be over-stated. Our findings may influence pediatric guidelines and thus the short- and long-term health outcomes in this large target group of newborns. We anticipate data from this study, including a cost analysis, will impact the manner in which donor milk is allocated in Canada and beyond. The existing relationships of the two supervisors for this project, [name] and [name], with policy makers at the World Health Organization, Health Canada, the Canadian Pediatric Society and Dietitians of Canada will facilitate rapid and effective

knowledge translation. We will utilize well established social media platforms such as Today's Parent, Life with a Baby and the Roger's Hixon Ontario Human Milk Bank Instagram and Facebook to message parent groups. The primary publication for this trial will be led by [name], the postdoctoral research fellow and will be targeted at a high impact open access journal such as the Canadian Nutrition Society's journal, Applied Physiology, Nutrition and Metabolism. Reports will be prepared for presentation at both national and international scientific conferences (for example, the International Society for Research in Human Milk and Lactation annual meeting) and parent webinars (for example, the Canadian Premature Babies Foundation webinar series).

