#### 1.8 Sample size estimation and power calculations

According to the systematic scoping review of McCune and Perrin published in January 2021, there are no data from RCTs comparing donor milk to formula for supplementation of late preterm or term newborns (13). The only available RCT is a pilot study that assessed the feasibility of using donor milk versus formula for a small group of 32 full-term and late preterm infants admitted to NICU; even though this study did assess certain aspects related to breastfeeding, such as feeding attempts and growth, the authors emphasized the need for larger-scale studies to validate the findings of this pilot study (15). The current exclusive breastfeeding rate in Toronto at 4 months of age is 28% (31). In one retrospective review following donor milk supplementation in late preterm and term newborns ( $\geq$ 35 weeks gestational age), the rate of exclusive breastfeeding rate to 56% would be clinically significant and plausible given the published data and was thus used for sample size calculation. With 80% power and an alpha level of 0.05, we require 47 infants in each of the two study arms. We anticipate, based on our prior work, a 15% loss to follow-up to 4 months of age (32); hence 56 infants will be recruited for each study arm or 112 infants in total.

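### Does section 1.15 promise too much when it says a trial sized for 28% versus 56% will support or refute wider access to donor milk?

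*Protocol*

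**What the plan says.** Section 1.15 (Expected project deliverables) opens with the claim "The proposed trial will provide enough data to either support or refute the need for improved access to donor milk in well-baby units". It then says that positive results could be used to argue for more equal access. For the opposite case it says that "null or negative trial results may call into question the use of donor milk for this population of infants" and that such results "may suggest redirection of funds to other programs within a well-baby unit". Each of these consequences is put as a possibility.

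Section 1.14 gives the background: a change in supplementation policy needs prior research because "it may be an important public health initiative, or it may be costly without benefit".

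The statistical basis is in section 1.8. The control rate is the Toronto figure of 28%, and the target is the "rate to 56% would be clinically significant and plausible given the published data and was thus used for sample size calculation". The result is stated as "With 80% power and an alpha level of 0.05, we require 47 infants in each of the two study arms". Allowing for 15% loss, 56 per arm are recruited. The primary objective in section 1.3.1 is one of superiority. The protocol states no equivalence margin, futility margin or smallest worthwhile effect.

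**The concern.** The opening sentence of 1.15 allows two outcomes only. A superiority trial of 47 evaluable infants per arm has a third: a non-significant difference whose confidence interval still contains a benefit worth having. The later hedges concern what might be done with the results, not whether the data will be sufficient.

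The risk is one of reading. Section 1.15 treats null and negative results together and mentions moving funds elsewhere. A reader who took the first sentence literally could treat an inconclusive result as evidence against donor milk, although such a result cannot separate the two possibilities named in 1.14.

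**Working it through.** **Inputs.** From section 1.8: control 28%, target 56% (difference 28 points), alpha 0.05, power 80%, 47 evaluable and 56 recruited per arm. From section 1.6.4: 1:1 allocation. Assumed: a two-sided test (the protocol does not state sidedness) and an unadjusted comparison of two proportions.

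**1. The protocol's sample size.** With mean rate 0.42,

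n = [1.96·√(2·0.42·0.58) + 0.842·√(0.28·0.72 + 0.56·0.44)]² / 0.28² = (1.368 + 0.563)² / 0.0784 ≈ 47.6.

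The arcsine formula gives 47.3. The stated 47 therefore reproduces to within rounding, and power at 47 per arm is 0.795 by the normal approximation. For loss, 47 / 0.85 = 55.3, so 56. The sizing is sound.

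**2. What a null result looks like.** If both observed rates are 28%, the half-width of the 95% interval is 1.96·√(2·0.28·0.72/47) = 0.182. The interval runs from about −18 to +18 points: it excludes the 28-point target but leaves smaller benefits open.

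With 13/47 in the formula arm:

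| Donor milk arm | p (pooled z) | Upper 95% limit, Wald / Newcombe | +28 excluded? |
|---|---|---|---|
| 13/47 | 1.00 | +18.1 / +17.7 | yes |
| 17/47 | 0.38 | +27.3 / +26.4 | yes |
| 18/47 | 0.27 | +29.5 / +28.5 | no |
| 22/47 | 0.055 | +38.3 / +36.8 | no |
| 23/47 | 0.034 | significant | not applicable |

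With this control count, the results that neither reach significance in favour of donor milk nor exclude the target run from 18 to 22 successes in the donor milk arm.

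**3. How often that happens.** Exact binomial enumeration over all pairs of counts, with a two-sided pooled z-test at 0.05. Entries are percentages of all trials; pairs are Wald / Newcombe.

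| | No effect, 47 per arm | True +28, 47 per arm | No effect, 56 per arm | True +28, 56 per arm |
|---|---|---|---|---|
| Significant for donor milk | 2.5 | 79.2 | 2.5 | 85.5 |
| Significant for formula | 2.5 | 0.0 | 2.5 | 0.0 |
| Non-significant, +28 excluded | 83.7 / 85.6 | 2.1 / 3.1 | 88.8 / 90.0 | 2.3 / 3.2 |
| Non-significant, +28 in interval | 11.2 / 9.4 | 18.7 / 17.7 | 6.1 / 5.0 | 12.2 / 11.2 |

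The last row is the share that neither supports nor refutes the sized effect. The 56-per-arm columns show the best case, with no loss to follow-up.

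**4. What the last row means.** Under a true +28, the non-significant share at 47 per arm is 20.8%, the type II error implied by 80% power. Of this, 18.7 points (Wald) keep +28 in the interval. Not refuting an effect that is real is the correct behaviour; the failure is in not detecting it, and section 1.8 discloses that rate. Only the no-effect column, 9 to 11%, measures a failure to refute.

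**5. Smaller effects.** With an assumed true benefit of 14 points (half the target), 70.5% of trials would be non-significant, and 40.2 / 36.9% of all trials would be non-significant with +28 still in the interval. These are the largest figures, but the 14 points are not from the protocol, which names no worthwhile effect below the target.

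**The case for a change.** The strongest case for acting is that the claim can be checked and, read literally, fails. At the two effects implied by the protocol, between roughly 1 trial in 10 and 1 in 5 would neither support nor refute the target. Excluding 28 points does not exclude smaller benefits: among non-significant trials under no effect, 60 to 61% would rule out 20 points and only 18% would rule out 10. Section 1.15 expects the results to reach policy makers quickly, and stating in advance how a null will be read protects against treating absence of evidence as evidence of absence. The remedy, saying that the trial will inform the question, costs nothing.

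The arithmetic stands, and so does the description of the sentence as too strong. The case for a change does not. No trial with 80% power can guarantee a decisive result, so that standard would fault almost any superiority trial. The 10-, 14- and 20-point values come from outside the protocol. A fuller rule, under which a null is inconclusive whenever its interval contains 28 points and any statement on funding rests on that interval, would go too far: section 1.8 uses 28 points for sizing, not as a decision threshold, and sections 1.14 and 1.15 tie policy also to costs and secondary outcomes. How a non-significant result is to be interpreted is commonly left to the SAP or the trial report, and the SAP is not at hand.

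**Conclusion.** The opening sentence of 1.15 is a mild overstatement and needs no change to the plan. At 47 evaluable infants per arm, 9 to 11% of trials under no effect and 18 to 19% under the target effect would be non-significant with +28 points still in the 95% interval. The second figure is mostly the type II error stated in 1.8. Otherwise the design does what a loose reading of the sentence promises: 79% of trials are significant under the target effect, and 84 to 86% are non-significant with the target excluded under no effect.

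The sentence is aspirational text in a deliverables section. No hypothesis, sample size, model, stopping decision or conduct depends on it, and the policy consequences that follow it are already conditional. Analysts will report an estimate with its confidence interval whatever this sentence says. Softer wording would be a harmless editorial choice with no effect on any result.

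The figures assume a 28% control rate, a two-sided 0.05 test and an unadjusted comparison. For an assumed control rate between 20% and 40%, the share of non-significant trials under no effect that exclude +28 ranges from 80 to 95%, so the conclusion does not depend on the exact rate.

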#### 1.16 Interactions

This project will be jointly led by the Rogers Hixon Ontario Human Milk Bank at Sinai Health in Toronto and the University of Toronto. The trial will take place in the well-baby unit at Sinai Health which admits >6000 newborns annually. The clinical trial will be under the direct supervision of [name] who is a neonatologist at Sinai Health and the medical director for the Rogers Hixon Ontario Human Milk Bank. [name] is also a member of the Departments of Pediatrics and Nutritional Sciences in the Temerty Faculty of Medicine at the University of Toronto. The Rogers Hixon Ontario Milk Bank, partially funded by the Ontario Ministry of Health and Long Term Care, is the only milk bank in Ontario. The milk bank has the capacity to process approximately 250 L of milk per week with the ability to scale up as required. It is anticipated that the study will require approximately 1 L of donor milk per week to meet the needs of trial participants. All human milk analyses (milk cortisol) will take place in [name] laboratory at the University of Toronto. In-person follow up visits at 4 months of age will take place at the Nutrition Intervention Centre at the University of Toronto located in the David Naylor Building, just a short walk from Mount Sinai Hospital.

#### 1.17 Study Steering Committee

The Steering Committee, consisting of the principal investigator, co-investigators, study coordinator, milk bank representative, and parent advisor/representative, will hold the authority for making decisions concerning the arrangement and execution of the trial. This committee has been entrusted with the responsibility of ensuring that the trial progresses smoothly and according to the set objectives.

To ensure effective collaboration and consistent decision-making, the Steering Committee will convene bi-monthly, twice a month, for the entire planned duration of the study. During these meetings, a wide range of topics will be discussed, including the study's progress, challenges faced, emerging findings, potential adjustments to methodologies, ethical considerations, participant engagement strategies, and more. This regular engagement ensures that the trial remains on track, ethical standards are upheld, and decisions are made collectively to achieve the study's objectives successfully.

